#### **9.5 Health-related outcomes and healthcare resource utilization**

Health-related outcomes and HRU will be collected in the eCRF and/or diary during the study according to the tabular schedule of assessments (Table 5-1).

These assessments will include:

- Socio-professional status
- Healthcare provider consultations not foreseen by the protocol including the type of provider (general practitioner, specialist physician, nurse), the site of care (office-private, office-hospital, home, emergency room), and the reason leading to the consultation
- Concurrent medical procedures
- Concomitant medications
- Hospitalizations including the reason leading to the hospitalization, admission ward transfers, and length of stay
- Caregiver support needs
- Number of school or working days lost due to the medical condition of the subjects

## 9.6 Treatment satisfaction

The Treatment Satisfaction Questionnaire for Medication (TSQM)-9 is a 9-item questionnaire developed to provide a suitable measure of treatment satisfaction with medication (Bharmal et al, 2009). It has 5 to 7 Likert response options per item and consists of 3 subscales: effectiveness (3 items), convenience (3 items), and a global satisfaction scale (3 items). The TSQM-9 was developed from the TSQM 1.42, which has an additional subscale that measures side effects (3 items) (Atkinson et al, 2004). The estimated completion time for this questionnaire is less than 5 minutes. Scores range from 0 (worst) to 100 (best).

The TSQM-9 will be completed according to the tabular schedule of assessments (Table 5-1). At the very beginning of the visit, the TSQM-9 will be provided to all subjects. It is preferred that the subject complete the questionnaire on his/her own; however, assistance may be provided by either the study staff or caregiver if needed. Once completed, the subject will return the completed questionnaire to the Investigator or designee, who will verify that all questions have been answered. Further details about the TSQM-9 will be covered in the Study Manual.

## 10 ASSESSMENT OF PHARMACOKINETIC VARIABLES

Blood samples for PK and exploratory variables will be obtained at the scheduled time points presented in Table 5-1 and details of the collection, storage, preparation, and shipping of samples will be presented in a Laboratory Manual.

### 10.1 Pharmacokinetic variables

The PK variables for PSL and [REDACTED] metabolite are described in detail in Section 4.3. Calculations of PK parameters will be made using population PK modeling. Additionally, plasma concentration data for concomitantly administered AEDs will be evaluated by comparing ratios of steady-state levels vs Baseline levels. For details of PK analyses, refer to Section 13.4.2.

Detailed information on the collection, storage, preparation, and shipping of samples will be presented in a Laboratory Manual.

#### 10.1.1 PK sampling procedures

##### 10.1.1.1 PSL assay

Subjects are requested to provide blood samples, via MITRA microsampling, for measurement of PSL and [REDACTED] metabolite levels whenever possible. Site personnel are requested to discuss the importance of PK samples to measure blood levels of PSL. Site personnel should educate subjects regarding the importance of accurately recording the time of the last IMP intake and their concomitant AEDs.

On Visits 3, 5, and 6, site personnel should obtain blood samples for random PSL levels at any time between IMP intakes and record accurately the time of last IMP intake and time of the sample.

On Visits 4 and 7, blood samples for measurement of sparse PK profiles should be collected as follows: immediately before IMP intake (maximum 15 minutes before intake) and then 3 times after (between 30 minutes and 3 hours after IMP intake) taken at least 30 minutes apart.

All samples may be taken either at home or at the site when possible or partly at home and partly at the site.

### **10.1.1.2 Concomitant AED and exploratory pharmacokinetic evaluation**

Subjects are requested to provide blood samples for a concomitant AED assay (to evaluate any DDI with PSL) at Visits 1, 2, 6, and 7.

On Visits 6 and 7, if the time point of sampling is not within 5 minutes of one of the scheduled PSL PK collections, then an additional blood sample, via MITRA microsampling, will be taken alongside ( $\pm 5$  minutes) the concomitant AED sample. This process will only be done at some pre-selected sites for a limited number of subjects.

Assay of PSL metabolites may be included in the concomitant AED assay screen. This analysis of PSL metabolites will not be conducted in Chinese subjects because it is exploratory.

## **11 ASSESSMENT OF SAFETY**

### **11.1 Adverse events**

#### **11.1.1 Definitions**

##### **11.1.1.1 Adverse event**

An AE is any untoward medical occurrence in a patient or clinical investigation subject administered a pharmaceutical product that does not necessarily have a causal relationship with this treatment. An AE can therefore be any unfavorable and unintended sign (including an abnormal laboratory finding), symptom, or disease temporally associated with the use of a medicinal (investigational) product, whether or not related to the medicinal (investigational) product.

In order to ensure complete safety data collection, all AEs occurring during the study (ie, after the signing of the ICF until the SFU Visit), including any pretreatment and posttreatment periods required by the protocol, must be reported in the eCRF even if no IMP was taken but specific study procedures were conducted. This includes all AEs not present prior to the initial visit and all AEs that recurred or worsened after the initial visit.

Signs or symptoms of the condition/disease for which the IMP is being studied (ie, seizures) should be recorded as AEs only if their nature changes considerably or their frequency or intensity increases in a clinically significant manner as compared to the clinical profile known to the Investigator from the subject's history or the Baseline Period.

##### **11.1.1.2 Serious adverse event**

Once it is determined that a subject experienced an AE, the seriousness of the AE must be determined. An SAE must meet 1 or more of the following criteria:

- Death
- Life-threatening  
(Life-threatening does not include a reaction that might have caused death had it occurred in a more severe form.)
- Significant or persistent disability/incapacity
- Congenital anomaly/birth defect (including that occurring in a fetus)

- Important medical event that, based upon appropriate medical judgment, may jeopardize the patient or subject and may require medical or surgical intervention to prevent one of the other outcomes listed in the definition of serious

(Important medical events may include, but are not limited to, potential Hy's Law [see Section 11.1.1.3], allergic bronchospasm requiring intensive treatment in an emergency room or at home, blood dyscrasias that do not result in inpatient hospitalization, or the development of drug dependency or drug abuse.)

- Initial inpatient hospitalization or prolongation of hospitalization

(A patient admitted to a hospital, even if he/she is released on the same day, meets the criteria for the initial inpatient hospitalization. An emergency room visit that results in admission to the hospital would also qualify for the initial inpatient hospitalization criteria. However, emergency room visits that do not result in admission to the hospital would not qualify for this criteria and, instead, should be evaluated for 1 of the other criteria in the definition of serious [eg, life-threatening adverse experience, important medical event].

Hospitalizations for reasons not associated with the occurrence of an AE [eg, preplanned surgery or elective surgery for a pre-existing condition that has not worsened or manifested in an unusual or uncharacteristic manner] do not qualify for reporting. For example, if a subject has a condition recorded on his/her medical history and later has a preplanned surgery for this condition, it is not appropriate to record the surgery or hospitalization as an SAE, since there is no AE upon which to assess the serious criteria. Please note that, if the pre-existing condition has worsened or manifested in an unusual or uncharacteristic manner, this would then qualify as an AE and, if necessary, the seriousness of the event would need to be determined.)

### 11.1.1.2.1 Anticipated serious adverse events

The following Anticipated SAEs are anticipated to occur in the population studied in this protocol at some frequency that is independent of drug exposure.

This list does not change the Investigator’s obligation to report all SAEs (including Anticipated SAEs) as detailed in Section 11.1.2.3.

**Table 11–1: Anticipated SAEs for the epilepsy population**

MedDRA System Organ Class	MedDRA Preferred Term
Congenital and hereditary disorders	Teratogenicity
General disorders and administration site conditions	Sudden unexplained death in epilepsy
Injury, poisoning, and procedural complication	Fall a , fracture a , injury a
Nervous system disorders	Cluster seizures, convulsion, incontinence a memory impairment, status epilepticus
Pregnancy, puerperium, and perinatal disorders	Abortion spontaneous
Psychiatric disorders	Abnormal behavior, acute psychosis, anxiety, cognitive disorder, confusional state, psychotic behavior, sleep disorder and disturbances
Reproductive system and breast disorders	Impotence, menstrual disorder

MedDRA=Medical Dictionary for Regulatory Activities, Version 19.1; SAE=serious adverse event;  
SOC=System Organ Class

a Events are anticipated when occurring in the context of seizure, but not classified in MedDRA primary SOC.

### 11.1.1.3 Adverse events of special interest

An AE of special interest is any AE that a regulatory authority has mandated be reported on an expedited basis, regardless of the seriousness, expectedness, or relatedness of the AE to the administration of a UCB product/compound.

Potential Hy’s Law, defined as  $\geq 3 \times \text{ULN}$  ALT or AST with coexisting  $\geq 2 \times \text{ULN}$  total bilirubin in the absence of  $\geq 2 \times \text{ULN}$  ALP, with no alternative explanation for the biochemical abnormality, must ALWAYS be reported to UCB as an AE of special interest (ie, without waiting for any additional etiologic investigations to have been concluded). Follow-up information should then be reported if an alternative etiology is identified during investigation and monitoring of the subject.

### 11.1.2 Procedures for reporting and recording adverse events

The subject will be given the opportunity to report AEs spontaneously. A general prompt will also be given at each study visit to detect AEs. For example:

“Did you notice anything unusual about your health (since your last visit)?”

In addition, the Investigator should review any self-assessment procedures (eg, diary cards) employed in the study.

### 11.1.2.1 Description of adverse events

When recording an AE, the Investigator should use the overall diagnosis or syndrome using standard medical terminology, rather than recording individual symptoms or signs. The eCRF and source documents should be consistent. Any discrepancies between the subject's own words on his/her own records (eg, diary card) and the corresponding medical terminology should be clarified in the source documentation.

Details for completion of the Adverse Event eCRF (including judgment of relationship to IMP) are described in the eCRF Completion Guidelines.

### 11.1.2.2 Rule for repetition of an adverse event

An increase in the intensity of an AE should lead to the repetition of the AE being reported with:

- The outcome date of the first AE that is not related to the natural course of the disease being the same as the start date of the repeated AE, and the outcome of "worsening"
- The AE verbatim term being the same for the first and repeated AE, so that the repeated AE can be easily identified as the worsening of the first one

### 11.1.2.3 Additional procedures for reporting serious adverse events

If an SAE is reported, UCB must be informed within 24 hours of receipt of this information by the site (see contact information for SAE reporting listed in the SAE Reporting section at the front of the protocol). The Investigator must forward to UCB (or its representative) a duly completed "Investigator SAE Report Form for Development Drug" (SAE Report form) provided by UCB, even if the data are incomplete, or if it is obvious that more data will be needed in order to draw any conclusions. Information recorded on this form will be entered into the global safety database.

An SAE Report form will be provided to the Investigator. The SAE Report form must be completed in English.

It is important for the Investigator, when completing the SAE Report form, to include the assessment as to a causal relationship between the SAE and the IMP administration. This insight from the Investigator is very important for UCB to consider in assessing the safety of the IMP and in determining whether the SAE requires reporting to the regulatory authorities in an expedited manner. Expedited reporting to regulatory authorities will be in line with local laws.

Additional information (eg, autopsy or laboratory reports) received by the Investigator must be provided to UCB within 24 hours. All documents in the local language must be accompanied by a translation in English, or the relevant information included in the same document must be summarized in the SAE Report form.

The Investigator is specifically requested to collect and report to UCB (or its representative) any SAEs (even if the Investigator is certain that they are in no way associated with the IMP), up to 6 months from the last IMP intake for each subject (ie, until the 6-month follow-up echocardiogram), and to also inform subjects of the need to inform the Investigator of any SAE within this period. Serious AEs that the Investigator thinks may be associated with the IMP must be reported to UCB regardless of the time between the event and the end of the study.

Upon receipt of the SAE Report form, UCB will perform an assessment of expectedness of the reported SAE. The assessment of the expectedness of the SAE is based on the IB.

### **11.1.3 Follow up of adverse events**

An AE should be followed until it has resolved, has a stable sequelae, the Investigator determines that it is no longer clinically significant, or the subject is lost to follow up. This follow-up requirement applies to AEs, SAEs, and AEs of special interest; further details regarding follow up of PDILI events is provided in Section 11.6.1.4.

If an AE is ongoing at the end of the study for a subject, follow up should be provided until resolution/stable level of sequelae is achieved, until the Investigator no longer deems that it is clinically significant, or until the subject is lost to follow up. If no follow up is provided, the Investigator must provide a justification. The follow up will usually be continued for 30 days after the subject has discontinued IMP.

Information on SAEs obtained after clinical database lock will be captured through the Patient Safety (PS) database without limitation of time.

## **11.2 Pregnancy**

If an Investigator is notified that a subject has become pregnant after the first intake of any IMP, the Investigator must immediately notify UCB's PS department by providing the completed Pregnancy Report and Outcome form (for contact details see SAE reporting information at the beginning of this protocol). The subject should be withdrawn from the study as soon as pregnancy is known (by positive pregnancy test), and the following should be completed:

- The subject should return for an EDV.
- The subject should immediately stop the intake of the IMP or be down-titrated as instructed at the EDV.
- An SFU Visit should be scheduled 1 week after the subject has discontinued her IMP.

The Investigator must inform the subject of information currently known about potential risks and about available treatment alternatives.

The pregnancy will be documented on the Pregnancy Report and Outcome form provided to the Investigator. The progression of the pregnancy and the eventual birth (if applicable) must be followed up using the Pregnancy Report and Outcome form in which the Investigator has to report on the health of the mother and of the child. Every reasonable attempt should be made to follow the health of the child for 30 days after birth for any significant medical issues. In certain circumstances, UCB may request that follow up is continued for a period longer than 30 days. If the subject is lost to follow up and/or refuses to give information, written documentation of attempts to contact the subject needs to be provided by the Investigator and filed at the site. UCB's PS department is the primary contact for any questions related to the data collection for the pregnancy, eventual birth, and follow up.

In cases where the partner of a male subject enrolled in a clinical study becomes pregnant, the Investigator or designee is asked to contact the subject to request consent of the partner via the Partner Pregnancy Consent form that has been approved by the responsible IRB/IEC and should be available in the Investigator site file. In case of questions about the consent process, the

Investigator may contact the UCB/contract research organization (CRO) contract monitor for the study. The Investigator will complete the Pregnancy Report and Outcome form and send it to UCB's PS department (for contact details see SAE reporting information at the beginning of this protocol) only after the partner has agreed that additional information can be captured and has provided the signed Partner Pregnancy Consent form. UCB's PS department is also the primary contact for any questions related to the data collection for the partner pregnancy, eventual birth, and follow up.

A pregnancy becomes an SAE in the following circumstances: miscarriage, abortion (elective or spontaneous), unintended pregnancy after hormonal contraceptive failure (if the hormonal contraceptive was correctly used), ectopic pregnancy, fetal demise, or any congenital anomaly/birth defect of the baby. Those SAEs must be additionally reported using the SAE Report form.

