### **4.2.2 Other safety variables**

Other safety variables are as follows:

- Incidence of TEAEs reported by the subject and/or caregiver or observed by the Investigator during the following periods: 16-week Treatment Period, 12-week Maintenance Period, 4-week Titration/Stabilization Period, and 3-week Taper Period
- Number of and reason for subjects requiring premature tapering due to TEAEs
- Number of and reason for subjects requiring a dose reduction during the Stabilization Period due to TEAEs
- Incidence of treatment-emergent SAEs during the following periods: 16-week Treatment Period, 12-week Maintenance Period, 4-week Titration/Stabilization Period
- Changes in clinical laboratory test parameters (including hematology, blood chemistry, and urinalysis)
- Changes in vital sign parameters (including pulse rate, SBP, DBP, and respiratory rate)
- Changes in 12-lead ECG parameters
- Physical examination (including body weight) and neurological examination findings
- Changes in Psychiatric and Mental Status exam
- Occurrence of valvular abnormalities or pericardial effusion changes or other significant abnormalities as identified by 2-dimensional Doppler echocardiogram at each assessment by central reader
- Changes in withdrawal symptoms using Clinical Institute Withdrawal Assessment-Benzodiazepines (CIWA-B) from the end of the 16-week Treatment Period (Visit 7) to the end of the Taper Period (Visit 8) and the end of the SFU Period (Visit 9 [30 days after the last IMP intake])

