#### Safety Follow-up Period (1 month)

Safety follow up for all subjects not entering the OLE will consist of 1 required visit, 30 days after the last IMP intake (Week 23 or sooner in case of early discontinuation), including an echocardiogram. An additional follow-up echocardiogram will be performed at 6 months ( $\pm 1$  month) after the last IMP intake only for subjects exposed to IMP for more than 3 weeks.

*For subjects continuing to the OLE study:*

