### **5.1.1 Study duration per subject**

The total duration of the study per subject will be up to 27 weeks with a maximum of 19 weeks exposure to PSL. An additional follow-up echocardiogram will be performed at 6 months ( $\pm 1$  month) after the last IMP intake only for subjects exposed to IMP for more than 3 weeks and either discontinuing the study or not entering the OLE.

The end of the study is defined as the date of the last SFU Visit (30 days after the last IMP intake) of the last subject in the study. Additionally, the reporting of SAEs will continue until the 6-month follow-up echocardiogram.

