e If an unscheduled visit is conducted due to safety or efficacy reasons, a C-SSRS assessment will be performed with the subject during the visit. If an unscheduled visit is conducted for reasons other than safety or efficacy concerns (eg, replacement of lost medication, repeated collection of a laboratory specimen due to collection, or analysis issues), a C-SSRS will not be required at these visits.

f Vital signs measured in supine position after 5 minutes of rest include pulse rate, respiratory rate, SBP, and DBP.

[figure not shown]
[figure not shown]
g Height will only be measured at Visit 1.

- h Full physical examinations will assess cardiac and respiratory function via auscultation and review of the following body systems: general appearance; ear, nose, and throat; eyes; hair and skin; respiratory; cardiovascular; gastrointestinal; musculoskeletal; hepatic; neurological; and mental status. Brief physical examinations will include a review of the following body systems: general appearance (including mental status); skin; respiratory; cardiovascular; gastrointestinal; and hepatic.
- i Brief neurological examination will include a general assessment and evaluation of reflexes, muscle strength and coordination, and cerebellar function. Full neurological examinations will include in addition, evaluation of cranial nerves, motor system (general muscle strength and tone), and sensations in upper/lower extremities.
- j Baseline ECG has to be scheduled and results received before Visit 2. An ECG at the SFU Visit will be performed only if abnormal at the End of Treatment or Early Discontinuation Visit. All ECG recordings will be performed with the subject resting in the supine position for at least 5 minutes.
- k The echocardiogram will be conducted at Visit 1. Echocardiograms will be repeated at Visit 6 for subjects continuing into the OLE study. Subjects discontinuing will have an echocardiogram 30 days after last IMP intake at the SFU Visit (except if performed at Visit 6). A repeat echocardiogram will be performed for subjects with a new finding, Grade 2 (moderate severity), or Grade 3 (severe severity).
- l An echocardiogram will also be performed 6 months after last IMP intake for subjects exposed to >3 weeks to IMP and discontinuing the study (but not for subjects with <3 weeks exposure).

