10. For subjects developing psychiatric/mood/behavioral signs or disturbances (see examples in list below) that are clinically concerning or that worsen over time, the subject should be referred immediately to a mental healthcare professional and must be withdrawn from the study.
  - Auditory or visual hallucinations
  - Delusions/paranoia/grandeur
  - Disorganized thought process
  - Agitation/aggression/apathy
  - Dysphoria/depression/mood lability/euphoria
  - Disinhibition
  - Cognitive changes/memory impairment/delirium
  - Aberrant motor behavior

11. Subject is suspected of having a serious multiorgan hypersensitivity reaction. Serious suspected multiorgan hypersensitivity cases may be identified and reported to the Sponsor by the Investigator using the following algorithm:
- An AE or laboratory value (as defined below) suggestive of internal organ involvement including but not limited to hepatitis, nephritis, pneumonitis, carditis, colitis, encephalitis, pancreatitis, myositis, arthritis, or hematologic system involvement, combined with at least 1 of the following: fever, rash, lymphadenopathy, or eosinophilia
  - Treatment-emergent abnormal laboratory value criteria suggestive of internal organ involvement or eosinophilia:
    - Eosinophils percentage  $\geq 10\%$
    - Eosinophils absolute  $\geq 0.5\text{G/L}$
    - Neutrophils absolute  $< 1.5\text{G/L}$
    - Platelets absolute  $\leq 100\text{G/L}$
12. There is confirmation of a pregnancy during the study, as evidenced by a positive pregnancy test.

Investigators should attempt to obtain information on subjects in the case of withdrawal or discontinuation. For subjects considered as lost to follow up, the Investigator should make an effort (at least 1 phone call and 1 written message to the subject), and document his/her effort (date and summary of the phone call and copy of the written message in the source documents), to complete the final evaluation. All results of these evaluations and observations, together with a narrative description of the reason(s) for removing the subject, must be recorded in the source documents. The eCRF must document the primary reason for withdrawal or discontinuation.

Investigators should contact the Medical Monitor, whenever possible, to discuss the withdrawal of a subject in advance.

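### Protocol 11.2 puts the Safety Follow-Up Visit 1 week after IMP stops in a subject withdrawn for pregnancy; elsewhere it is 30 days after last intake, with no pregnancy exception

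*Protocol*

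**What the plan says.** Protocol 11.2 sets three steps once a pregnancy is known. The subject returns for an Early Discontinuation Visit, she stops IMP at once or is down-titrated, and then: "An SFU Visit should be scheduled 1 week after the subject has discontinued her IMP". The visit is not numbered, and nothing says whether it replaces Visit 9 or is added to it.

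The other places in the protocol that time this visit give 30 days:

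- Section 1 (Summary): one SFU Visit, 30 days after last intake.
- Section 5.1, Safety Follow-up Period: "Safety follow up for all subjects not entering the OLE will consist of 1 required visit, 30 days after the last IMP intake".
- Section 5.1.1, in the definition of the end of the study: "the date of the last SFU Visit (30 days after the last IMP intake".
- Section 8.4 (Visit 9): about 30 days after last intake, ±7 days, explicitly including early discontinuations.
- Table 5-1 footnote k: "Subjects discontinuing will have an echocardiogram 30 days after last IMP intake at the SFU Visit", unless the echocardiogram was done at Visit 6.

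SAP 10.2 likewise ends AE recording with an SFU period of 30 days after last intake.

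**The concern.** Two sites could each follow the protocol and see the same kind of subject on days more than three weeks apart. The difference matters because of what is attached to the SFU Visit. Protocol 11.1.1.1 collects AEs up to that visit, and Section 8.4 closes the diary and lists study termination there. If the 11.2 visit is taken as the single SFU Visit, the final off-drug laboratory tests, examinations and psychiatric assessment are done at Day 7, and collection of new non-serious AEs may end then. Section 11.2 also allows IMP to be stopped without a taper, and Section 2.3.1 mentions a potential withdrawal syndrome. Some off-drug observation therefore has a purpose, although the Phase 1 withdrawal events are described there as mild and short-lived.

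**Working it through.** No figure in the plan needs reproducing. The check sets the passages side by side and counts days from last IMP intake (Day 0).

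1. **Does the general rule cover her?** Withdrawal criterion 12 in Section 6.3 reads "There is confirmation of a pregnancy during the study, as evidenced by a positive pregnancy test". She is therefore withdrawn. Only subjects completing the Maintenance Period are offered the extension, so she falls under the Section 5.1 rule for all subjects not entering it.

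2. **Does the early-discontinuation wording relax the interval?** Section 5.1 adds "Week 23 or sooner in case of early discontinuation". That moves the study week, because last intake comes sooner. The 30 days stay in the same sentence, and Section 8.4 keeps them in the same heading. The day numbers in Table 5-1 agree for a subject who completes treatment and tapers over 3 weeks:
   - last intake: 112 + 21 = Day 133
   - Visit 8 (Taper): 140 − 133 = 7 days after last intake
   - Visit 9 (SFU): 161 − 133 = 28 days after last intake, within 30 ± 7

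3. **How far apart are the two rules?**
   - permitted range under Section 8.4: 30 − 7 = Day 23 to 30 + 7 = Day 37
   - Section 11.2: Day 7
   - nominal difference: 30 − 7 = 23 days
   - distance to the earliest permitted day: 23 − 7 = 16 days

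4. **What does the protocol place at Day 7?** Section 5.1 (Taper Period) brings subjects back 1 week after last intake for Visit 8, the End of Taper Visit. Section 8.3.2 gives that visit its own laboratory tests and full examinations. The timing in 11.2 therefore matches Visit 8 and not Visit 9, which suggests a wrong label.

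5. **Can one visit satisfy both rules?** No. Section 5.1 provides one required SFU visit, and footnote k puts the 30-day echocardiogram at it. A single visit at Day 7 cannot meet footnote k unless the echocardiogram was already done at Visit 6.

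6. **What could be lost?** If the 11.2 visit replaces Visit 9, new non-serious AEs from about Day 7 to Day 30 (23 days) may go uncollected, and there is no Day 30 laboratory or examination record. If it is additional, the loss is zero.

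**The case against.** The strongest reply is that the passages can be reconciled. Section 11.2 uses the indefinite article and no visit number, whereas 11.7.3 names Visit 9 when it means that visit. One required visit is a minimum, and Section 8.5 allows extra visits at any time. An early pregnancy check plus Visit 9 at Day 30 would satisfy every passage. That may be what was intended, but 11.2 does not say so, and it uses the defined term for the visit at which Section 8.4 lists study termination.

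Three stronger readings are tempting, and the documents do not support them.

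- A reader might infer that every cited section fixes a 30 (±7)-day window. The ±7 days for the visit appear only in Section 8.4 and the Table 5-1 window row, with ±1 week for the echocardiogram in 11.7.3. Sections 1, 5.1 and 5.1.1, footnote k and SAP 10.2 say 30 days without a window. The conflict does not depend on this.
- A reader might infer that withdrawal-scale (CIWA-B) data are compromised for a subject who stops at once. Table 5-1 footnote d restricts the CIWA-B to subjects who taper, so she would have no score to displace. The point is relevant only for a subject who tapers, and she is already due a CIWA-B at Visit 8, about Day 7.
- A reader might infer that AE data will be lost. Three places argue otherwise: 11.1.1.1 includes required posttreatment periods, Section 5.1 describes a 1-month follow-up period, and SAP 10.2 runs to 30 days. The echocardiogram rule would also bring most such subjects back near Day 30. The loss is possible, not established.

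**Conclusion.** The inconsistency is real and minor. Section 11.2 gives sites an instruction that lies 16 days outside the earliest day allowed elsewhere, no text makes a pregnancy exception, and the timing suggests that Visit 8 was meant.

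The consequence is conditional. It arises only if a site treats the 11.2 visit as its sole SFU Visit, and it is then limited to the Day 30 laboratory tests, examinations and new non-serious AEs. Other follow-up is covered separately: SAEs for 6 months (11.1.2.3), ongoing AEs (11.1.3), the 30-day and 6-month echocardiograms where they apply (11.7.3), and pregnancy outcome (11.2 itself). No efficacy analysis changes.

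The day counts assume that stopping IMP in 11.2 means last intake. The documents give no number of affected subjects. Few are expected, given the contraception requirement and repeated pregnancy testing. The SAP records early termination, so only follow-up still open could be affected.

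**What to change.** Replace the third bullet of Protocol 11.2 with:

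> The SFU Visit (Visit 9) should be scheduled 30 days (±7 days) after the last IMP intake, as for all subjects not entering the OLE; a visit 1 week after the last intake (Visit 8, End of Taper, if she is down-titrated, or an extra safety visit if she stops at once) is additional and does not end AE collection.

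This keeps an early check if one was intended. It costs one sentence in the protocol. The SAP can stay as it is, because SAP 10.2 already uses 30 days, and no analysis changes.
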